1.5.1.1. OS RATE AT 1 YEAR vs BASAL CHARACTERISTICS

A univariate and multivariate analysis of the possible association between baseline characteristics and the rate was presented below. of global survival per year, using logistic regression models taking death per year as an event.

Table 22. Univariate analysis: 1-year OS rate vs characteristics baseline

		1-year OS			Univariate logistic regression	
		No (death) N (%)	Yes (alive) N (%)	Total N (%)	OR (95% CI)	p -value
Age categorized according to median (66 years)	<66 years					
	≥66 years					
	Total					
Sex	Female					
	Male					
	Total					
KPS	90-100					
	70-80					
	Total					
Barthel Index	15-20					
	<15					
	Total					
Status B-Raf (Current Melanoma)	Native					
	Mutated					
	Total					
No. of lines of previous treatment	> 1					
	1					
	0					
	Total					
Status B-Raf (previous Melanoma)	Native					
	Mutated					
	Total					
Type of locations M1 Current	brain Single					
	Multiple					
	Total					
Location M1 Current liver	No					
	Yes					
	Total					
Corticosteroids at baseline and / or C1	No					
	Yes					
	Total					
No. of organs with metastatic disease	1					
	2					
	3					
	4					

	Total	
No. of organs with metastatic disease	≤2	
	> 2	
	Total	
Neutrophil /Ratio Lymphocyte(quantitative)		
Neutrophil /ratio Lymphocyte> 3 (high risk)	No	
	Yes	
	Total	
Previous BRAF Inhibitor	No	
	Yes	
	Total	
CRP value		
Hemoglobin value		
LDH value		
LDH value> ULN	No	
	Yes	
	Total	
LDH value> 1.5 * ULN	No	
	Yes	
	Total	

1.5.1.2. 1-YEAR OS RATE vs BASAL CHARACTERISTICS. MULTIVARIATE ANALYSIS Baseline

Table 23. Multivariate analysis: 1-year OS rate vs characteristics

		Multivariate logistic regression		
		N ¹	OR (95% CI)	p-value
XXXXX	No			
	Yes			
Constant				

1: patients for whom no data were available are excluded from the model data in all variables included in the multivariate model (n = X).

In the table below, the variables that were not significant have been excluded:

Table 24. Multivariate analysis: 1-year OS rate vs characteristics²

		Multivariate logistic regression		
		N ¹	OR (95% CI)	p-value
BaselineXXXXXI	No			
	Yes			

1: patients for whom data were not available on all variables included in the multivariate model (n = X) are excluded from the model.

2: IMPORTANT NOTE: Those variables that were not significant but that were used for the construction of the multivariate model shown in the table are not shown in the table *previous*.

Table 25. Multivariate analysis: 1-year OS rate vs characteristics baseline

		Multivariate logistic regression		
		N ¹	OR (95% CI)	p-value
XXX	No			
	Yes			
Constant				

1: patients for whom no data was available in all variables included in the multivariate model (n = X).

1.5.1.3. 1-YEAR SG RATE vs BASAL CHARACTERISTICS. MULTIVARIATE ANALYSIS. GOODNESS OF FIT

Table 26. Goodness of fit: Hosmer-Lemeshow

	Chi-square test	Degrees of freedom	p-value
Hosmer and Lemeshow Test			

Table 27. Goodness of fit: Classification table

		Predicted OS at 1 year		
		No (death)	Yes (alive)	% correct
OS at 1 year	No (death)			
	Yes (alive)			

% Total

Table 28. Goodness of fit: Area under the curve

AUC	Standard error	p-value	95% CI
-----	----------------	---------	--------

Figure 2. Goodness of fit: ROC curve

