PD, SD, or no data	CR* or PR*	Any	CR or PR (at 12 weeks)
PD, SD, CR**, PR** or no data	SD, CR**, PR**	CR* or PR*	CR or PR (at time point after Week 12)
PD, SD, PR**, CR** or no data	SD, PR**, CR**	PD, SD, PR**, CR** or no data	SD
SD, PR**, CR** or no data	PD	Any	PD (at Week 12)
PD	PD	Any	PD (at time point before Week 12)

* Initial OR of PR or CR confirmed by a second (confirmatory) evaluation meeting the criteria for response and performed no less than 4 weeks after the criteria for response are first met.

** OR of PR or CR not confirmed by a second (confirmatory) evaluation meeting the criteria for response and performed no less than 4 weeks after the criteria for response are first met.

6.4.2.h Local Radiotherapy for Symptomatic Bone Lesions

Local radiation treatment to the site of bone metastasis will be permitted for palliative pain management at any time during the study but it is encouraged that the Investigator perform this local radiotherapy following consultation with the Medical Monitor and the Week 12 following re-staging assessments (ie, Week 16, confirmatory assessments).

6.4.2.i Response Kinetics and Immune-related Endpoints

Ipilimumab is expected to trigger immune-mediated responses, which require activation of the immune system prior to the observation of clinical responses. Such immune activation may take weeks to months to become evident. Some subjects with advanced melanoma may have objective volume increase of tumor lesions within 12 weeks following start of ipilimumab dosing. These subjects may not have had sufficient time to develop the required immune activation or, in some subjects, tumor volume increases may represent infiltration of lymphocytes into the original tumor. In conventional studies, such tumor volume increases during the first 12 weeks of the study would constitute PD and lead to discontinuation of imaging to detect response, thus disregarding the potential for subsequent immune-mediated clinical response. Therefore, in this study, subjects with tumor volume increase detected prior to Week 12 but without rapid clinical deterioration will continue to be treated with ipilimumab and clinically observed with a stringent imaging schedule to allow detection of a subsequent tumor response until progression is confirmed at the subsequent timepoint. Such assessments will be using identical criteria, considering

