9.4.5 Exploratory Analyses

Two types of ALC analyses will be done: pharmacodynamic and predictive. Both analyses will include all treated subjects with known date of first dose of ipilimumab. Pharmacodynamic analyses will examine the patterns of change in ALC over time, and how these patterns might differ between treatment arms. Predictive analyses will examine potential relationships between ALC and measures of response such as overall survival.

The proposed biomarker study includes analysis of tumor tissue at diagnosis and serum/peripheral blood at different phases within the treatment schedule. All analysed parameters will be correlated with progression-free survival (PFS), overall survival and histopathological parameters.

For the statistical analysis, it will be used binary variables, reflecting the positivity status of the measures (yes or no; presence/absence). Association with histopathological parameters. The significance level will be set at 5%. To study the impact of the histological, immunohistochemical and molecular factors on progression-free survival (PFS) and overall survival (OS), the Kaplan-Meier proportional risk test (log rank) will be used. Evidence of the relative risk for each patient will be also provided by means of a Cox proportional hazards model using stepwise selection to identify the independent predictors of poor outcome.

For the kinetic profile of the serum/blood biomarkers, each variable will be considered as continuous. A correlation at different points of the treatment schedule will be considered and the slope value will be used in order to distinguish those cases with no change, negative or positive trend. The threshold will be calculated after considering the behavior of the whole series.

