1.5.2.1. PFS RATE A 6 MONTHS vs BASAL CHARACTERISTICS

Next, a univariate and multivariate analysis was proposed. e the possible association between the baseline characteristics and the 6-month progression-free survival rate, using logistic regression models taking PD or death as an event at 6-month follow-up.

A univariate analysis was carried out in which none of the following variables showed a statistically significant association ($p < 0.1$) with PFS at 6 months of follow-up and therefore multivariate analysis was not carried out.

Table 32. Univariate analysis: PFS rate at 6m vs Baseline characteristics

		PFSat 6m		Univariate logistic regression		
		No (without PD or death) N (%)	Yes (living without PD) N (%)	Total N (%)	OR (95% CI)	p-value
Age categorized according to median (66 years)	<66 years					
	≥66 years					
	Total					
Sex	Female					
	Male					
	Total					
KPS	90-100					
	70-80					
	Total					
Barthel Index	15-20					
	<15					
	Total					
Status B-Raf (Current Melanoma)	Native					
	Mutated					
	Total					
No. of lines of previous treatment	0					
	1					
	> 1					
	Total					
Status B-Raf (previous Melanoma)	Native					
	Mutated					
	Total					
Type of locations M1 Current Brain	Single					
	Multiple					
	Total					
Location M1 Current liver	No					
	Yes					
	Total					
Corticosteroids at baseline and / or C1	No					
	Yes					
	Total					

No. of organs with metastatic disease	1	
	2	
	3	
	4	
	Total	
No. of organs with metastatic disease	≤2	
	> 2	
	Total	
Neutrophil / Lymphocyte(quantitative)		
RatioNeutrophil /Ratio Lymphocyte> 3 (high risk)	No	
	Yes	
	Total	
Previous BRAF Inhibitor	No	
	Yes	
	Total	
CRPvalue		
Hemoglobinvalue		
LDH valueLDH value		
> ULN	No	
	Yes	
	Total	
LDH value> 1.5 * ULN	No	
	Yes	
	Total	

-

Table 33 Multivariate analysis: PFS rate at 6m vs Baseline characteristics

		Multivariate logistic regression		
		N ¹	OR (95% CI)	p-value
XXXXXX	No			
	Yes			
XXXXXX	No			
	Yes			
Constant				

1: patients for whom data were not available in all variables included in the multivariate model (n = X).

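### The SAP screens 16 baseline factors against 1-year death in about 56 patients and reports the model's AUC on those same patients; noise alone would give a mean AUC of about 0.70–0.75 whenever a model is fitted

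*SAP*

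**What the plan says.** SAP 1.5.1.1 announces univariate and multivariate analyses of 1-year survival "using logistic regression models taking death per year as an event", in the evaluable population. Each row of Table 22 carries an odds ratio and a p-value. LDH appears as a value, above ULN and above 1.5 × ULN. The neutrophil/lymphocyte ratio and the number of organs with metastases appear twice each. Age is split at a median already given as 66 years.

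Multivariable tables follow in 1.5.1.2 (Tables 23–25). The line before Table 24 reads "In the table below, the variables that were not significant have been excluded". Its footnote 2 reads "Those variables that were not significant but that were used for the construction of the multivariate model shown in the table are not shown". Footnotes to Tables 23–25 remove patients with missing data on any model variable.

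Section 1.5.1.3 assesses the model by a Hosmer-Lemeshow test, a classification table, "Table 28. Goodness of fit: Area under the curve" and a ROC curve.

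For PFS, 1.5.2.1 states a p<0.1 screen, reports no association "with PFS at 6 months of follow-up and therefore multivariate analysis was not carried out", and still carries the shell "Table 33 Multivariate analysis: PFS rate at 6m vs Baseline characteristics". No AUC is planned there.

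Protocol 9.4.5 handles histological and molecular factors separately, "by means of a Cox proportional hazards model using stepwise selection to identify the independent predictors of poor outcome".

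**The concern.** Two things combine. First, many candidate factors are tested against a small outcome group, and several are tested in more than one coding, so chance associations are likely to enter the model. Second, the AUC is computed on the patients who determined which factors entered. It therefore rewards the selection and cannot show whether the model would discriminate in anyone else.

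A report built from these tables could present a chance factor as an independent predictor of 1-year survival, supported by an AUC that looks clinically useful. The p-value and confidence interval in Table 28 would not warn the reader, because nothing in the supplied text says they allow for the selection.

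The text also leaves unclear which OS model is being judged. It gives no entry threshold, and it does not settle whether the variables missing from Table 24 leave the model or only the display.

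**Working it through.** **The plan's own figure.** Protocol 9.1 gives n = 56, success at 17 or more alive, and rates of 20% and 35%. Exact binomial: P(X ≥ 17 | 0.20) = 0.0432 and P(X ≥ 17 | 0.35) = 0.8064. The design is reproduced, and nothing below touches it.

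**Information available.** 56 × 0.20 = 11.2 and 56 × 0.35 = 19.6, so about 11–20 patients are in the smaller group. Per factor: 11/16 = 0.7 to 20/16 = 1.25. Complete-case exclusion would reduce this further.

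**Chance findings before modelling** (16 independent tests). At least one p<0.05: 1 − 0.95^16 = 0.56. At least one p<0.1: 1 − 0.90^16 = 0.81.

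**Simulated null trials.** Assumptions not in the SAP: entry at p<0.1 for OS (borrowed from PFS), significance at p<0.05, Wald tests, 16 pure-noise factors, n = 56, and assumed factor prevalences. Each setting used 1,500–2,000 trials. AUC is the mean among trials that produced a model.

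| Setting | Alive | Significant factor, terms kept | Significant factor, terms eliminated | Mean same-data AUC |
|---|---|---|---|---|
| Mixed factor types, within-block correlation 0 / 0.3 / 0.7 | 20% | 0.367 / 0.373 / 0.287 | 0.419 / 0.440 / 0.401 | 0.70–0.74 (both rates) |
| Same | 35% | 0.459 / 0.442 / 0.336 | 0.515 / 0.514 / 0.472 | as above |
| Mixed, independent | 11 | – | 0.455 | 0.740 |
| Same | 20 | – | 0.533 | 0.707 |
| Same, with the four repeat codings added | 11 | – | 0.478 | 0.744 |
| Same, with the four repeat codings added | 20 | – | 0.596 | 0.714 |
| All continuous, independent | 11 | – | 0.507 | 0.753 |
| Same | 20 | – | 0.515 | 0.716 |

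In the all-continuous setting the mean AUC on new data was 0.50. The upper end of the elimination range, 60%, comes from adding the repeat codings.

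**Conditioning.** In one set of null trials, 21%–27% produced no model. Scoring those as 0.50 gives 0.73 × 0.74 + 0.27 × 0.50 = 0.675 and 0.79 × 0.71 + 0.21 × 0.50 = 0.666. So the mean over all trials is about 0.66–0.68, while 0.70–0.75 describes what would be seen when Table 28 can be filled in.

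**Which correction works** (screened null models, correlation 0.3; OS 20% and 35%):
- Apparent AUC: 0.740 and 0.714.
- Bootstrap that only refits the chosen terms: 0.714 and 0.691, about 0.69–0.72 allowing for variation between runs.
- Bootstrap that repeats the screen: 0.604 and 0.578. A second set gave 0.610 and 0.579. The overall range is about 0.57–0.61.

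**A fixed list instead.** With two noise factors and no selection, the chance of any logistic p<0.05 is about 9% (formula: 1 − 0.95² = 9.8%). The AUC is 0.59–0.62 apparent and 0.52–0.55 corrected.

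**The case against.** The work is exploratory. SAP 1.5.1.1 speaks only of possible association, and the primary rule does not depend on it. That stands, and it limits the weight of the point. It does not make an uncorrected AUC informative.

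The entry rule is an assumption, and the opening part of the SAP was not available. A threshold or a validation step may be stated there. That also stands, so the figures are conditional.

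On Table 24, footnote 2 suggests that the terms are hidden rather than dropped. The absence of a Constant row, present in Tables 23 and 25, fits a display extract. The lower range (30%–47%) may therefore be the relevant one. The role of Table 25 is unexplained, so the question is not closed.

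A reader might infer more than the documents support:

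- **That noise gives a mean AUC as high as 0.77.** Only one set of assumed prevalences reached that; the rest give 0.70–0.75.
- **That Cox regression should replace logistic regression.** The primary endpoint is the actual 1-year proportion (Protocol 9.3.1), and the 6-month PFS rate is a named secondary endpoint (Protocol 2.2). Logistic models address both. Cox has more power under a constant hazard ratio of 2 (0.687 against 0.556 at OS 20%; 0.663 against 0.514 at 35%). With no effect for three months and HR 2 after that, the comparison is mixed (0.395 against 0.403; 0.459 against 0.363). With HR 3 in months 3–12 only, logistic is better (0.784 against 0.663; 0.748 against 0.593). This is a trade-off and has no bearing on the optimism problem.
- **That PFS shares the defect equally.** The text reports no multivariable PFS model, and no AUC is planned. Table 33 is an editorial leftover.

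**Conclusion.** The concern holds for the OS models. As written, the plan can readily produce a nominally significant predictor and a same-data AUC that looks useful when no factor has any effect. If entry is at p<0.1 and all 16 factors are noise, about 77% of null trials yield a model with a mean apparent AUC of about 0.70–0.75. The chance of a significant multivariable factor is roughly 30%–47% with non-significant terms kept in the model and 40%–60% with elimination.

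These figures rest on 56 evaluable patients, 11–20 of them alive at one year, and assumed factor prevalences and correlations. The SAP leaves the evaluable number blank. The absence of a correction is a statement about the supplied text only. The change is worth making, but the trial's conclusion on 1-year survival does not hang on it.

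**What to change.** For the OS models in SAP 1.5.1.1–1.5.1.3:

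1. Enter each factor once, in one stated form.
2. Use a short multivariable list justified on outside evidence, with no significance-based selection. KPS and number of brain metastases are an example: Protocol 1.2.1 reports them as the only significant factors among 481 patients. Check first that the single-metastasis group is not too sparse, since exclusion 1d removes some of these patients. Otherwise, state the selection rule and say whether variables absent from Table 24 leave the model or only the display.
3. Say whether the list was chosen without sight of outcomes. The SAP already holds result remnants: a median age of 66, a mean LDH of 420.3 U/L, counts in Table 51, and the PFS screening result.
4. Replace or accompany the Table 28 AUC with a bootstrap optimism-corrected value that repeats every selection step, or omit the AUC. Refitting only the chosen terms is not enough. Even the full correction leaves some optimism under the null (about 0.57–0.61 against 0.50), which favours the fixed list.
5. Label these models exploratory.

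Keep logistic regression for the 1-year and 6-month endpoints. Cox may be added as a supplement, and it can use patients without one-year follow-up, for whom Table 19 has a separate row. Table 33 should be deleted or explained.

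The cost is modest re-programming, some SAP wording, and a lower reported discrimination.

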10.5. Institutional Review Board/Independent Ethics Committee (IRB/IEC)

10.6. Records Retention

11. REFERENCE S

APPENDIX 1 KARNOFSKY PERFORMANCE STATUS SCALE

APPENDIX 2 BARTHEL INDEX OF ACTIVITIES OF DAILY LIVING

11. REFERENCE S

PROTOCOL SYNOPSIS

Protocol Title:	GEM 1202 A MULTICENTER, SINGLE ARM, PHASE 2 CLINICAL STUDY ON THE COMBINATION OF RADIATION THERAPY AND IPILIMUMAB, FOR THE TREATMENT OF PATIENTS WITH MELANOMA AND BRAIN METASTASES.
Short Title	GRAY-B (GEM STUDY RADIATION AND YERVOY IN PATIENTS WITH MELANOMA AND BRAIN METASTASES)
EUDRACT STUDY NUMBER	2013-001132-2
Country (ies) and Site Numbers.	Spain, 12 sites (Appendix 3)
Research Hypothesis:	
Ipilimumab adds a clinical benefit to radiation therapy in patients with melanoma metastatic to the brain.
 
 • Melanoma is the third most common cancer causing brain metastases, after cancers of the lung and breast, which appears to reflect the relative propensity of melanoma to metastasize to the central nervous system (CNS). Brain metastases are responsible for 20 to 54 percent of deaths in patients with melanoma, and among those with documented brain metastases, these lesions contribute to death in up to 95 percent of cases, with an estimated median overall survival ranging between 1.8 and 10.5 months, depending upon other prognostic factors. • Ipilimumab is an anti-CTLA4 monoclonal antibody that has demonstrated a clinically relevant and statistically significant improvement in overall survival, either alone (second line) or in combination with DTIC (1st line). • Ipilimumab has shown activity against brain metastases • According to the EMA-approved label for Yervoy[®], the use of glucocorticoids at baseline (commonly prescribed when brain metastases are diagnosed) should be avoided before the administration of ipilimumab. Data show that the use of even high doses of glucocorticoids for the management of immune-related adverse events do not decrease the efficacy of Yervoy[®]. There is no documented experience on the efficacy of Yervoy[®] when given concomitantly with radiation therapy and glucocorticoids. • In experimental models, radiation therapy is synergistic to anti-CTLA-4 strategies (abscopal effect) • There are no published results from clinical trials on the interaction between radiation therapy and ipilimumab.

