- Main eligibility criteria are: patients with melanoma and brain metastases, adequately fit (ECOG PS 0 to 1; Barthel Index > 10/20) and of intermediate prognosis according to the RPA classification (Table 1). These patients must not have cerebral metastases for which local therapy (neurosurgery, radiosurgery) might achieve a disease-free status; they must not be experiencing a rapid clinical deterioration, risk of herniation; patients must not require unstable ascending dosing of supportive medication in the last week -including anti-convulsivants, steroids and analgesics-, or dexamethasone > 16 mg/day (or other glucocorticoid at an equivalent dose); patients must not have a high LDH (> 2 x ULN), they must not have an uncontrolled diabetes mellitus (HbA1c > 9%) and must be suitable for receiving an anti CTLA4 (i.e. not having any autoimmune-mediated co-morbidities). Patients must have not received prior therapy for brain metastases. Screening stage: Once the ICF is signed by the patient and investigator, patients will be sequentially registered at the Spanish Melanoma Group Datacenter or delegated CRO, by submitting a “registration form”. A Patient Identification Number will be provided by the Sponsor. A second form, the “eligibility checklist”, will be sent by the investigational site once the screening phase has been completed, either if the patient becomes eligible or if he/she results in a screening failure. No protocol exceptions will be permitted by the sponsor.

Patient inclusion:

[figure not shown]
After confirming that a patient is a candidate for inclusion in this study (inclusion / exclusion), the subject will be assigned a code of patient centralized (registration or inclusion of patients).

The process of enrolling patients described below:

1. Complete and sign the inclusion of the patient (the registration form must be signed by a clinical Principal Investigator or designated appropriately identified in the list of signatures and recording studio delegation of responsibilities).
2. Send the completed and signed form to:

██
██

3. ██████████ will register the patient and
 4. will send the inclusion confirmation form to the site, both by fax and email. Confirmation of patient inclusion will contain the patient number, which identifies subjects in the trial.
 5. Once the site has received the confirmation of inclusion for the patient, the patient can begin receiving protocol treatment.

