Laboratory tests are obtained as part of screening and to determine eligibility. Results of safety laboratory collections (ie, Chemistry and Hematology) must be obtained and reviewed in advance of study drug dosing.

- The following lab parameters must be collected within a window of up to 1 day prior to dosing: CBC/diff (includes ANC and ALC), AST, ALT, total bilirubin, CRP, sodium, chloride, bicarbonate, BUN

or urea, creatinine, and glucose. Baseline values up to 7 days before the first dose are acceptable prior to C1. These lab tests will also be performed at week 12, EOT, and 90 days after last dose administration of ipilimumab (+/-1 week).

- CBC/diff, AST, ALT, total bilirubin, sodium, chloride, BUN or urea, creatinine, and glucose will also be collected weekly during WBRT

All protocol-specified laboratory tests will be analyzed and reported by a local lab.

Importantly, **LFT results (AST, ALT, and total bilirubin) must be reviewed within 24 h prior to dosing**. If abnormal LFTs are detected, the subject must be managed using the hepatotoxicity algorithm in the SMPC. (Additional draws must be incorporated when monitoring recovery from any non-hematologic AE (eg, elevations in ALT, AST).

6.4.1.f Endocrine Tests

The following endocrine tests should be performed at Screening and prior to each dosing visit: TSH, free T4 and T3, morning ACTH and cortisol, and prolactin.

Other hormones might be tested as well as clinically indicated.

During treatment, if patient is asymptomatic, it will be adequate to confirm at least the normality of the results of the tests performed within the last 3 weeks. If the patient is symptomatic (e.g. asthenia, cephalgia) it will be mandatory to check the results of the pre-dose testing (at least 72 h prior to dose administration)

6.4.1.g HIV and Hepatitis Panel

At screening, testing for HIV, hepatitis C antibody, and hepatitis B surface antigen (HBsAg) should be performed for clinically suspected HIV, HBV, and HCV. If positive results at Screening are not indicative of true active or chronic infection, the subject may enter the study after discussion and agreement between the Investigator and the Medical Monitor. These tests will be repeated during the course of the study if clinically indicated.

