Creatinine Clearance (ml / min)			
SGOT / AST (U / L)			
SGTP / ALT (U / L)			
Total Bilirubin (mg / dL)			
CRP			
Ureic Nitrogen or Urea (mg / dL)			
Glucose (mg / dL)			
Sodium (mmol / L)			
Chloride (mmol / L)			
Bicarbonate (mmol / L)			
Baseline LDH (U / L)			

Table 11. LDH categorized

		N (% ¹)
Value of LDH > ULN	No	
	Yes	
	Total	
LDH value > 1.5 * ULN	No	
	Yes	
	Total	

1:% with respect to *included patients* with available data.

Table 12. Baseline analysis: Endocrine

	N	Mean (SD)	Median (Min-Max)
Cortisol (ug / dl)			
ACTH (pg / mL)			
T4 (ug / mL)			
T3 (ug / mL)			
TSH (uIU / mL)			
Prolactin (ng / ml)			

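### Baseline factors are related to OS and PFS only by logistic regression at fixed times; adding Cox models, LDH scaled to the local ULN and CRP in one unit would recover precision at little cost

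*SAP*

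**What the plan says.** SAP 1.5.1.1 plans univariate and multivariate analyses of baseline characteristics against 1-year survival, "using logistic regression models taking death per year as an event". Sections 1.5.1.2 and 1.5.1.3 carry the same model through to Hosmer-Lemeshow and ROC output. SAP 1.5.2.1 treats PFS in the same way, "using logistic regression models taking PD or death as an event at 6-month follow-up". OS and PFS themselves are also described by Kaplan-Meier (SAP 1.5.1 and 1.5.2), but without baseline factors.

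Protocol 9.4.5 plans log-rank tests and "a Cox proportional hazards model using stepwise selection" for PFS and OS, in a paragraph about histological, immunohistochemical and molecular factors.

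Table 22 of the SAP has continuous rows for LDH and CRP. Table 10 gives LDH as "Baseline LDH (U / L)" and CRP without a unit. Protocol 6.4.1.e states: "All protocol-specified laboratory tests will be analyzed and reported by a local lab". The synopsis lists "Spain, 12 sites". Table 22 also has two LDH rows already scaled to the ULN, one of them "LDH value> 1.5 * ULN". Eligibility in protocol section 3 uses that scale too: "patients must not have a high LDH (> 2 x ULN)".

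**The concern.** A yes/no outcome at 12 or 6 months ignores the order of events before the cut and every event after it. A patient censored before the cut has no natural place in the model. Table 19 of the SAP sets such patients aside when it reports the crude 1-year rate, but the SAP does not say whether the logistic models do the same.

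What is at stake is precision. A real prognostic factor is more likely to be missed, and the multivariate model rests on the smaller outcome class. In SAP 1.5.2.1 a screen at p < 0.1 decides whether a multivariate model is fitted at all, so low power there has consequences.

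For the continuous LDH row, pooling U/L values from laboratories with different reference limits would mix laboratory differences with patient differences. CRP pooled in mixed units would have the same problem.

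**Working it through.** **Inputs from the documents.** Protocol 9.1: n = 56 evaluable, 1-year survival S of 20% (null) and 35% (target), success at 17 or more survivors. Protocol section 3: the study ends 18 months after the last patient's first dose, with at most 36 months per patient. The synopsis dates (last patient first visit 10/2015, follow-up 10/2016) imply only 12 months, so 12 to 36 months is covered.

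**Assumptions.** Exponential survival, proportional hazards, a 50/50 factor with hazard ratio 2, uniform accrual over 20 months, two-sided 5% tests.

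**The plan's own figure.** The exact binomial with n = 56 and cut-off 17 gives P(X ≥ 17 | 0.20) = 0.0432 and P(X ≥ 17 | 0.35) = 0.806. The design reproduces with a one-sided test.

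**Information kept.** Let H = −ln S at 1 year. Per patient, 1-year status carries information H²·S/(1−S) on the log hazard ratio. A Cox model with follow-up to t years carries information proportional to the event fraction, 1−S^t.

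- S = 0.20: H = 1.609, so 2.590 × 0.25 = 0.648.
- S = 0.35: H = 1.050, so 1.102 × 0.538 = 0.593.

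| Cox follow-up | Kept, S = 0.20 | Kept, S = 0.35 |
|---|---|---|
| 12 months | 0.648/0.800 = 0.81 | 0.593/0.650 = 0.91 |
| 18 months | 0.648/0.911 = 0.71 | 0.593/0.793 = 0.75 |
| 24 months | 0.648/0.960 = 0.68 | 0.593/0.878 = 0.68 |
| 36 months | 0.648/0.992 = 0.65 | 0.593/0.957 = 0.62 |

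The loss is therefore 9–19% within year 1 and 25–38% with 18–36 months of follow-up.

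**Power, n = 56, hazard ratio 2.** Simulation with censoring between 18 and 36 months gave:

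- S = 0.20: Cox 0.70, logistic 0.57, mean deaths 53.5.
- S = 0.35: Cox 0.67, logistic 0.52, mean deaths 49.6.

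A normal approximation agrees. For S = 0.20, Cox: Φ(0.693 × √(53.5/4) − 1.96) = Φ(0.575) = 0.72. Logistic: Φ(0.693 × √(56 × 0.648/4) − 1.96) = Φ(0.13) = 0.55.

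**Size of the smaller class.** Survivors at 1 year number 56 × 0.20 = 11.2 to 56 × 0.35 = 19.6. Cox would use about 50–54 deaths. Table 22 offers about 20 candidate rows.

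**Raw LDH.** The documents give no laboratory ULNs. Assume 12 laboratories, log-SD of LDH/ULN between 0.25 and 0.45, and truncation at 2 × ULN. The mean squared correlation between raw and scaled LDH is then:

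| Highest/lowest ULN | Squared correlation | Lost |
|---|---|---|
| 1.0 | 1.00 | none |
| 1.3 | 0.92–0.96 | 4–8% |
| 2.0 | 0.63–0.79 | 21–37% |

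For a hazard ratio of 1.5 per SD (log-SD 0.35), logistic power with scaled against raw LDH was 0.57–0.60 against 0.53–0.57 at a 1.3-fold spread, and 0.59–0.61 against 0.46–0.47 at 2-fold. Cox with scaled LDH reached 0.76–0.81 across the spreads tried.

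**The case against.** The logistic models match the endpoints. The primary endpoint is the proportion alive at 1 year (protocol 9.1, 9.3.1, 9.4.2.1), and the 6-month PFS rate is a listed secondary endpoint. A model of who reaches those landmarks is coherent, and deaths after 12 months lie outside that question. This stands, and it is why the logistic models should stay.

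Proportional hazards favours Cox. With no effect for 4 months and a hazard ratio of 3 afterwards, at 20% 1-year survival, simulated power was 0.72 for logistic against 0.69 for log-rank. This also stands, although at 35% survival with such a delay the time-to-event test stayed 12–14 points ahead.

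A reader might infer three stronger things that the documents do not support:

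- That most of the time-to-event information is thrown away. It is not: 62–91% is kept over the range above, because 65–80% of patients are expected to die within the year.
- That the SAP departs from a Cox analysis required by protocol 9.4.5. That paragraph concerns biomarker-type factors. B-Raf status and CRP arguably fall under it, but age, performance status and the other clinical rows do not.
- That LDH enters only in raw units and its effect is therefore attenuated. Two rows of the same table are scaled to the ULN. For the continuous row the attenuation depends on ULNs that are not given. The missing CRP unit is a blank in a table shell and does not show that values will be pooled unconverted.

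**Conclusion.** The point holds as an inexpensive improvement to secondary analyses. Relying on logistic regression alone costs about a quarter to three eighths of the available information with 18–36 months of follow-up, or 13–15 points of power at a hazard ratio of 2 (0.70 − 0.57 and 0.67 − 0.52). It also leaves the multivariate model resting on 11–20 patients in its smaller class. These figures assume exponential proportional hazards. If follow-up stopped at 1 year the information loss would be 9–19%, and delayed effects could remove or reverse the power gap.

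The LDH and CRP part is about good practice. Its size is unknown, and it is nil for LDH if the laboratories share one ULN. Neither the 17-of-56 decision rule nor the safety analysis is touched. The opening part of the SAP, before section 1.2, was not available, so a method stated only there cannot be ruled out.

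**What to change.** - In SAP 1.5.1.1–1.5.1.3 and 1.5.2.1, add univariate and multivariate Cox regression of OS and PFS from the first ipilimumab dose, using the SAP's existing censoring rules, with a proportional-hazards check. Keep the logistic models alongside for the 1-year and 6-month endpoints.
- State how the logistic models treat patients censored before 12 or 6 months.
- Enter the continuous LDH row as a multiple of the local laboratory's ULN. The two categorical LDH rows already need that limit.
- Convert CRP to one common unit and print it in Tables 10, 22 and 32.

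The cost is SAP wording, some extra programming and a second set of secondary results to report. No new data are needed beyond the laboratories' CRP units.
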